9.1.2 Management of Diarrhea during Systemic Treatment prior to Chemoradiation

- Early Diarrhea (e.g., developing in less than 24 hours after irinotecan infusion:
Lacrimation, rhinorrhea, miosis, diaphoresis, hot flashes, flushing, abdominal cramping, diarrhea, or other symptoms of early cholinergic syndrome may occur during or shortly after receiving irinotecan. Atropine, 0.25-1. mg IV or SC may be used to treat these symptoms. In patients with troublesome or recurrent symptoms, prophylactic administration of atropine shortly before irinotecan therapy may be considered. Additional antidiarrheal measures may be used at the discretion of the treating physician. Combination anticholinergic medications containing barbiturates or other agents (e.g., Donnatal®) should not be used because these may affect irinotecan

metabolism. Anticholinergics should be used with caution in patients with potential contraindications (e.g., obstructive uropathy, glaucoma, tachycardia, etc.).

- Late Diarrhea (e.g., developing more than 24 hours after irinotecan infusion):
Manage with loperamide, as per standard of care guidelines and package insert for irinotecan. Dose modifications are based on toxicity experienced at any time during a cycle.

Patients should be optimally managed with anti-diarrheal medications before dose modifications are made.

9.1.3 SBRT Toxicities and Potential Risks

Prior studies investigating 25 Gy given in a single fraction resulted in a combined Grade 3 or higher toxicity in 8% of patients. In our recently completed multi-center Phase II study, we did not observe significant toxicities related to SBRT with a dose of 33 Gy in 5 fractions.

In another recent study of SBRT for unresectable locally advanced pancreas cancer, with a prescription dose of 45Gy (7.5 Gy in 6 fractions), no Grade ≥ 3 toxicities were reported and FFLP was $\geq 91\%$ at 6 months.(29)

Given these recently reported data of improved FFLP and no increase in toxicity, the SBRT prescription dose will be 40 Gy (in 5 fractions of 8 Gy).

Hepatic and renal toxicity is not anticipated given the expectation of limited incidental irradiation of these organs and we have not observed any to date in the patients treated with SBRT. Complications, if any, will be graded according to CTCAE v4.0 or higher.

10. DRUG FORMULATION, AVAILABILITY, AND PREPARATION

Qualified personnel who are familiar with procedures that minimize undue exposure to themselves and to the environment should undertake the preparation, handling, and safe disposal of chemotherapeutic agents in a self-contained, protective environment. Chemotherapy treatment is standard-of-care and can be administered at any qualified medical facility.

Discard unused portions of injectable chemotherapeutic agents that do not contain a bacteriostatic agent or are prepared with unpreserved diluents (i.e., Sterile Water for Injection USP or 0.9% Sodium Chloride for Injection USP) within eight hours of vial entry to minimize the risk of bacterial contamination.

The total administered dose of chemotherapy may be rounded up or down within a range of 5% of the actual calculated dose.

10.1 Oxaliplatin

Please refer to the package insert for complete product information.

Availability

Oxaliplatin is commercially available a solution in vials containing 50 mg, 100 mg, and 200mg at a concentration of 5 mg/mL. The vials do not contain any preservative and they are intended for single use.

Storage and Stability

Intact vials should be stored at room temperature. According to the manufacturer, solutions diluted in D5W are stable for 6 hours at room temperature or 24 hours under refrigeration. Solutions diluted in D5W to a concentration of 0.7 mg/mL are reported to be stable (sterility not tested) for up to 30 days at room temperature or under refrigeration.

Preparation

The calculated dose of oxaliplatin should be diluted for infusion with 250 mL to 500 mL D5W. Oxaliplatin should not be diluted with a chloride-containing solution. Needles, syringes, catheters or IV administration sets containing aluminum should not be used with oxaliplatin. As with other platinum compounds, contact with aluminum may result in a black precipitate.

Administration

Oxaliplatin will be administered by intravenous infusion over 2 hours prior to irinotecan, and prior to or concurrent with leucovorin. Infusion time may be prolonged (up to 6 hours) in patients experiencing pharyngolaryngeal dysesthesia.

Toxicity

The most commonly observed oxaliplatin toxicities include neurotoxicity, GI toxicity, and myelosuppression. Three neurotoxicity syndromes have been seen: acute sensory neuropathy develops within hours to 2 days after oxaliplatin administration. Symptoms include, paresthesias, dysesthesias, and hypothesia of the hands, feet and perioral region. Jaw spasm, abnormal tongue sensation, dysarthria, eye pain and a sensation of chest pressure have also been noted. Acute sensory neuropathy symptoms may be exacerbated by exposure to cold temperature or cold objects. Symptoms are reversible, usually resolving within 14 days and commonly recurring with further dosing. This syndrome has been observed in about 56% of patients receiving oxaliplatin with 5-FU and leucovorin.

Acute pharyngolaryngeal dysesthesia is reported to occur in 1-2% of patients. This syndrome is characterized by a subjective sensation of difficulty breathing or swallowing without laryngospasm or bronchospasm or objective evidence of hypoxia. Avoidance of cold drinks, food and air is suggested in order to minimize pharyngolaryngeal dysesthesia. Antianxiety agents (e.g., lorazepam) may be used to treat pharyngolaryngeal dysesthesias once oxygen saturation has been documented to be normal.

Peripheral neuropathy persisting > 14 days is characterized by paresthesias, dysesthesias, and hypothesia. Abnormalities in proprioception may also be seen. Symptoms of persistent neuropathy may improve upon discontinuation of oxaliplatin.

Various agents have been used in an attempt to minimize neurotoxicity of oxaliplatin (e.g. carbamazepine, Mg⁺, Ca⁺⁺). Calcium and magnesium infusions appear to be beneficial in preventing neurotoxicity. Contrary to preliminary findings described in

2007, calcium and magnesium do not appear to interfere with tumor response to FOLFOX. Calcium and magnesium infusions are generally given before and after oxaliplatin, and should not be prepared in the same infusion solution as FOLFOX or FOLFIRINOX components.

Gastrointestinal toxicities include nausea, vomiting (oxaliplatin is considered to be moderately emetogenic) and diarrhea. Grade 3 or 4 neutropenia was reported in 46% of patients receiving FOLFIRINOX, and grade 3 or 4 thrombocytopenia was reported in 9%.

Allergic reactions, similar to those seen with other platinum compounds, have also been observed in patients treated with oxaliplatin. Reactions range from rash to anaphylaxis.

Rarely, oxaliplatin has been associated with pulmonary fibrosis, which may be fatal. Oxaliplatin should be discontinued in the presence of unexplained pulmonary symptoms (e.g. nonproductive cough, dysphagia) or pulmonary infiltrates until interstitial lung disease or pulmonary fibrosis have been ruled out.

Recent reports of oxaliplatin extravasation suggest that tissue necrosis may result and that oxaliplatin should be considered a vesicant. No standard treatment exists for oxaliplatin extravasation although heat and sodium thiosulfate have both been suggested.

Veno-occlusive disease (VOD) of the liver is a rare complication associated with oxaliplatin and 5-FU. Clinical manifestations of VOD include hepatomegaly, ascites, and jaundice. Histologically, VOD is characterized by diffuse damage in the centrilobular zone of the liver. Sequelae of VOD include hepatomegaly, splenomegaly, portal hypertension, and esophageal varices. A recent analysis of resected liver metastases in 153 patients indicated histological findings consistent with VOD in 6/27 patients who received 5-FU alone, 4/17 patients who received 5-FU and irinotecan, 20/27 patients who received 5-FU and oxaliplatin, and 14/16 who received 5-FU, oxaliplatin and irinotecan. The remaining 66 patients had not received chemotherapy prior to resection. There were no such findings in these patients.

For more information on toxicities associated with oxaliplatin, please see the package insert.

10.2 5-Fluorouracil (5-FU)

Please refer to the package insert for complete product information.

Availability

5-FU is commercially available as a 50 mg/mL solution for injection in 10 mL, 20 mL, 50 mL and 100 mL vials.

Preparation

Inspect for precipitate; if found, agitate or gently heat in water bath.

46-48 hour infusion of 5-FU should be prepared for administration via ambulatory infusion pump according to the individual institution's standards. These solutions may be prepared in D5W or 0.9% NaCl. 5-FU should not be mixed in the same solution with most parenteral antiemetics.

Storage and Stability

Intact vials should be stored at room temperature and protected from light. Slight yellow discolor does not usually indicate decomposition. Stability in ambulatory pumps varies

according to the pump, manufacturer of drug, concentration and diluent. Please refer to appropriate reference sources for additional information.

Administration

In this study, 5-FU is administered as an IV infusion over 46 – 48 hours. There is no bolus injection of 5-FU.

Toxicity

GI: Nausea, diarrhea, vomiting (mild); stomatitis: 5-8 days after treatment initiation; Myelosuppression: neutropenia (9-14 days); thrombocytopenia (7-14 days);

Dermatologic: Alopecia; nails changes; vein pigmentation; photosensitivity; maculopapular rash; palmar–plantar erythrodysesthesias,

CNS effects: cerebral ataxia (rare);

Cardiotoxicity: MI, angina; asymptomatic S–T changes;

Ocular effects: excessive lacrimation and less commonly, tear duct stenosis.

Drug Interactions

Leucovorin enhances the cytotoxicity of 5-FU by forming a more stable tertiary complex with thymidylate synthase. Concomitant administration of 5-FU with warfarin has been reported to result in increased INR/prolonged prothrombin time.

10.3 Leucovorin Calcium (Folinic Acid) (calcium folinate; citrovorum factor; N 5-formyltetrahydrofolate; 5-formyl-FH₄; folinic acid)

Please refer to the package insert for complete product information.

Availability

Leucovorin calcium is commercially available in 50 mg, 100 mg, 200 mg, and 350 mg vials for reconstitution, and 50 mL vials of solution at a concentration of 10 mg/mL.

Storage and Stability

Intact vials of powder for reconstitution should be stored at room temperature and protected from light. Solutions reconstituted with bacteriostatic water for injection are stable for up to 7 days at room temperature. Solutions reconstituted with sterile water for injection should be used immediately.

Intact vials of solution should be stored under refrigeration and protected from light.

Solutions further diluted for infusion are stable for 24 hours at room temperature, and 4 days under refrigeration.

Preparation

Leucovorin may be reconstituted with Bacteriostatic Water for Injection or with Sterile Water For Injection. Solutions should be further diluted in D5W, 0.9% NaCl or Ringers solution for IV infusion over two hours.

Administration

Leucovorin will be administered as a 400 mg/m² IV infusion over 2 hours after, or concurrent with, oxaliplatin and irinotecan. For administration concurrent with oxaliplatin (30 minutes) and irinotecan (90 minutes), leucovorin is administered as a separate infusion (i.e, not in the same IV solution).

Toxicity

The only adverse reactions associated with leucovorin are allergic reactions. These are

rare.

10.4 Irinotecan (CPT-11, CAMPTOSAR®)

Please refer to the package insert for complete product information.

Availability

Irinotecan is commercially available as a 20 mg/mL solution for injection in 2 mL and 5 mL vials.

Storage and Stability

Intact vials should be stored at controlled room temperature 59° to 86° F (15° to 30° C) and protected from light. Solutions diluted in D5W are reported to be stable for 24 hours at room temperature, or 48 hours under refrigeration and protected from light.

Preparation

Irinotecan is diluted in 5% dextrose (D5W) 500 mL to a final concentration of 0.12 – 2.8 mg/mL. Stability is improved in D5W as compared with NaCl.

Administration

In this study irinotecan will be administered as an IV infusion over 90 minutes, following oxaliplatin, and prior to, or concurrent with, leucovorin.

Toxicities

Neutropenia and/or late diarrhea (diarrhea occurring more than 24 hours after irinotecan administration) are frequently dose-limiting. Other commonly observed adverse events include nausea and vomiting, anorexia (irinotecan is considered moderately emetogenic), abdominal cramping, alopecia, asthenia, lymphocytopenia, and anemia. Dehydration has occurred as a consequence of diarrhea, particularly when associated with severe vomiting. Patients may experience an acute syndrome of lacrimation, diaphoresis, abdominal cramping, and diarrhea (early diarrhea) during or shortly after irinotecan administration; this syndrome is thought to be cholinergically mediated and may be treated and subsequently prevented with atropine. Elevations of bilirubin and alkaline phosphatase have been reported in up to 84% and 13% of patients, respectively. Sporadic cases of pulmonary toxicity, manifested as shortness of breath, nonproductive cough, and transient infiltrates on chest X-ray have been reported. Infrequent occurrences of mucositis or colitis (sometimes with gastrointestinal bleeding) have been observed. Irinotecan is metabolized to Sn-38, an active metabolite. SN-38 is conjugated by UGT1A1. Homozygosity for the UGT1A1*28 allele increases the risk of severe neutropenia with irinotecan, and known homozygotes are not eligible for this trial. Further information regarding irinotecan may be obtained from the package insert.

11. ADVERSE EVENTS, UNANTICIPATED PROBLEMS, AND DEVIATIONS

As Coordinating Center, we will follow guidelines from Stanford's Research Compliance Office and Cancer Clinical Trials Office (CCTO) for defining, identifying, and reporting events as defined below.

11.1 Serious Adverse Events (SAEs)

A Serious Adverse Event (SAE) is defined as: Any adverse event that meets any of the following criteria:

- Fatal (i.e., the adverse event actually causes or leads to death)
- Life threatening (i.e., the adverse event, in the view of the investigator, places the patient at immediate risk of death). This does not include any adverse event that had it occurred in a more severe form or was allowed to continue might have caused death
- Requires or prolongs inpatient hospitalization
- Results in persistent or significant disability/incapacity (i.e., the adverse event results in substantial disruption of the patient’s ability to conduct normal life functions)
- Congenital anomaly/birth defect in a neonate/infant born to a mother exposed to study drug
- Significant medical event in the investigator's judgment (e.g., may jeopardize the patient or may require medical/surgical intervention to prevent one of the outcomes listed above).(28)

11.1.1 Reporting SAEs

SAEs should be graded according to the NCI Common Terminology Criteria for Adverse Events, Version 4.0, available at <http://ctep.cancer.gov/reporting/ctc.html>.

SAEs Grade 3 and above require prompt reporting – within 24 hours of learning of the event. Reporting should be done by entering the event into OnCore (Stanford’s clinical trials management system) and sending an email to [Stanford Cancer Clinical Trials Office \(CCTO\) at [contact]](mailto:[contact]), copying [name] and Stanford research staff (Research Nurse or Research Coordinators) with subject line: “SECURE: PanCRS STUDY Serious Adverse Event.” A Case Report Form (CRF) describing the event must be supplied and can be sent as an attachment to the email. It could be generated from the OnCore entry (as a pdf or report), or using the Case Report Form in Appendix V.

Stanford research staff will notify Stanford IRB via ‘eProtocol’ as per regulatory guidelines. The SAE may also be forwarded to other Stanford regulatory boards, e.g., DSMC, as applicable.

Any questions, issues, or need for clarification of the event by Stanford IRB will go through Stanford study PIs or Coordinators to the participating center research staff.

Participating centers are responsible for reporting the SAE to their IRB within their institutional timeframes and guidelines.

Participating sites should also:

- Place copies of the SAE Report in the patient’s study chart and in the regulatory binder (electronic regulatory binder is allowed).

- Follow patient and provide update to Stanford until any of the below:
 - Resolution of event
 - Resolution of event with sequelae
 - Death of patient

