Another phase II study treated locally advanced pancreatic cancer patients with gemcitabine followed by 25 Gy of SBRT delivered with Cyberknife and maintenance gemcitabine chemotherapy. In this study, the excellent progression free survival was confirmed from previous studies (81%). The median overall survival was 11.4 months, median time to progression was 9.7 months and 1 year survival was 50%(14). There were no significant acute GI toxicities however, of the 15 patients alive >6 months after SBRT, 7 (47%) experienced Grade 2 or greater GI toxicity, with 2 (13%) of the 15 experiencing Grade 3 or greater GI toxicity.

More recently, another phase II study of 25 Gy in a single fraction using a linac-based approach (Trilogy™, Varian Medical Systems, Palo Alto, CA) integrated with gemcitabine chemotherapy resulted in a 50% overall survival at 1 year and a 94% freedom from local progression at 1 year. Four patients (15%) developed Grade 2 ulcers and 1 patient (5%) developed a duodenal perforation (Schellenberg et al, IJROBP 2011).

Recently, we completed a multi-center phase II trial demonstrating the efficacy of SBRT (33

Gy in 5 fractions) in combination with gemcitabine chemotherapy. No significant toxicities were observed and median overall survival was 18 months. These data compare favorably to other studies reported in the literature. Based upon these promising data, we hypothesize that adding SBRT to a more aggressive systemic chemotherapy (FOLFIRINOX), will result in further improvement in OS in patients with locally advanced pancreatic cancer.

The proposed randomized study is a logical extension of the previously reported studies and will establish the efficacy of adding SBRT to FOLFIRINOX chemotherapy. Our prior multi-center phase II experience demonstrated the feasibility and efficacy of this approach in patients with locally advanced pancreatic cancer.

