11.2 Unanticipated Problems (UPs)

Per Stanford IRB, UPs are events involving risks to participants or others and must meet ALL 3 criteria below:

1. **Unexpected:** in terms of nature, severity, or frequency, given (a) the research procedures described in the protocol-related documents, and (b) the characteristics of the subject population being studied; AND
2. **Related to participation in the research:** or there is a reasonable possibility that the incident, experience, or outcome may have been caused by the procedures involved in the research; or if a device is involved, probably caused by, or associated with the device; AND
3. **Harmful:** suggests that the research places subjects or others at a greater risk of harm (including physical, psychological, economic, or social harm) than was previously known or recognized.

UPs generally will warrant consideration of substantive changes in the research protocol or informed consent process/document, or other corrective actions, in order to protect the safety, welfare, or rights of subjects or others. (27) Due to this, UPs will be reported promptly to Stanford IRB following the below guidelines.

A UP may also be an AE or SAE and can be noted as both on CRFs and in OnCore.

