11.2.1 Reporting UPs

UPs should be entered into OnCore and reported [within 24 hours of learning of the event. Reporting can be done via email to Stanford Cancer Clinical Trials Office \(CCTO\) at \[[contact]\]\(mailto:[contact]\), copying [name] and Stanford research staff \(Research Nurse or Research Coordinators\), with subject line: "SECURE: PanCRS STUDY Unanticipated Problem."](#) A Case Report Form (CRF) describing the event must be supplied and can be sent as an attachment to the email. It could be generated from the OnCore entry (as a pdf or report), or using the Case Report Form in Appendix V.

Stanford research staff will notify Stanford IRB via 'eProtocol' as per regulatory guidelines. The UP may also be forwarded to other Stanford regulatory boards, e.g., DSMC, as applicable.

Any questions, issues, or need for clarification of the UP by Stanford IRB will go through Stanford study PIs or Coordinators to the participating center research staff.

Participating centers are responsible for reporting Unanticipated Problems or similar events to their IRB within their institutional timeframes and guidelines.

Participating sites should also:

- Place copies of the UP Report in the patient’s study chart and in the regulatory binder (electronic regulatory binder is allowed).
- Follow patient and provide update to Stanford until any of the below:
 - Resolution of event
 - Resolution of event with sequelae
 - Death of patient

SAE and UP Reporting Requirements				
Hospitalization	Grade 1	Grade 2	Grade 3	Grade 4/5
Hospitalization ≤ 24 hrs	UP's within 24 hours	UP's within 24 hours	Report SAE and UP within 24 hours	Report SAE and UP within 24 hours
Hospitalization ≥ 24 hrs	UP's within 24 hours	UP's within 24 hours	Report SAE and UP within 24 hours	Report SAE and UP within 24 hours

SAE Definition: Fatal, life threatening, requires hospitalization or prolongs hospitalization, results in persistent or significant disability, causes congenital anomaly/birth defect or significant medical event.
				

Unexpected Problem (UP) Definition: Unexpected in terms of nature, severity, or frequency. Related to participation in the research. And Harmful suggesting that the research places subjects or others at a greater risk of harm.
				

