
To report all UP's and SAEs Grade 3 and above: 1)Enter the event into OnCore, 2)send email to [name] and Stanford research staff ([name]) with the subject line: "SECURE: PanCRS STUDY Serious Adverse Event" and 3)Include Case Report Form describing the event and submit follow up reports for the resolution of the event. For any questions regarding whether an event is an SAE or a UP, please email [name] and [name].
				

[name]: [contact] [name]: [contact]
				

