Protocol: *Pancreatic Cancer Radiotherapy Study Group (PanCRS) Trial: A Randomized Phase III Study Evaluating Modified FOLFIRINOX (mFFX) with or without Stereotactic Body Radiotherapy (SBRT) in the Treatment of Locally Advanced Pancreatic Cancer*

Stanford eProtocol #: 27492

OnCore #: PANC0015

Participating Center: _____

Subject Log

#	Subject Name	Subject Initials	Subject ID or OnCore #	Date On-Study (Date of Randomization)	Treatment Arm	Treatment Start Date (Day 1)	Date Off-Study	Reason Off-Study
1					 mFFX  +SBRT			
2					 mFFX  +SBRT			
3					 mFFX  +SBRT			
4					 mFFX  +SBRT			
5					 mFFX  +SBRT			
6					 mFFX  +SBRT			

7					 mFFX  +SBRT			
8					 mFFX  +SBRT			
9					 mFFX  +SBRT			
10					 mFFX  +SBRT			

Protocol: Pancreatic Cancer Radiotherapy Study Group (PanCRS)

Trial: A Randomized Phase III Study Evaluating Modified FOLFIRINOX (mFFX) with or without Stereotactic Body Radiotherapy (SBRT) in the Treatment of Locally Advanced Pancreatic Cancer

Stanford eProtocol #: 27492

OnCore #: PANC0015

Participating Center: _____

Protocol Deviation Log

#	Subject Initials	Subject ID or OnCore #	Date of Deviation	Category (see next page)	Code (see next page)	Brief Description	Date IRB notified, if applicable	Corrective Action
1								
2								
3								
4								

5								
6								
7								
8								
9								
10								
11								
12								

Deviation Categories

- A. Safety
- B. Informed Consent
- C. Eligibility
- D. Protocol Implementation
- E. Other, specify in log

Deviation Codes (associated with Deviation categories)

Safety (Category A)

1. Not reporting SAE within 24 hours
2. Laboratory tests not done
3. AE/SAE not reported to IRB
4. Other, specify on log

Informed Consent (Category B)

5. Failure to obtain informed consent
6. Consent form used was not current IRB approved version
7. Consent form does not include updates or information required by IRB
8. Consent form missing
9. Consent form not signed and dated by participant

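### The plan sets inconsistent grade thresholds for prompt reporting of serious adverse events, so a serious grade 1–2 event that is not an unanticipated problem has no 24-hour route and the route of a grade 3 SAE is unclear

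*Combined protocol and SAP*

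**What the plan says.** Section 11.1 makes an event serious on its outcome. The definition opens with "Any adverse event that meets any of the following criteria", and one criterion is "Requires or prolongs inpatient hospitalization". None of the criteria refers to CTCAE grade.

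Section 11.1.1 sets the duty to report to the coordinating center: "SAEs Grade 3 and above require prompt reporting", within 24 hours of learning of the event. The SAE and UP reporting table in 11.2.1 has one row for shorter and one for longer hospitalization. In both rows the grade 1 and grade 2 cells read "UP's within 24 hours", and SAE reporting begins in the grade 3 column. The instruction below the table has the same limit: "To report all UP's and SAEs Grade 3 and above".

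Section 11.2 restricts the UP route: "UPs are events involving risks to participants or others and must meet ALL 3 criteria below". The three criteria are unexpected, related and harmful.

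Section 17.5.1 says, with a reference to Section 11, that grade 4 and higher events are reported promptly to the coordinating center. Grade 3 and lower adverse events are kept on logs at each site and reported on request.

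In Appendix V, the first deviation code, under Safety, is "Not reporting SAE within 24 hours", with no grade attached.

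**The concern.** Seriousness and severity are different scales. The plan defines SAEs on the first and then filters their reporting on the second, at two different cut-offs. Two groups of events are affected.

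- **Serious grade 1–2 events that are not UPs.** They meet the SAE definition but have no 24-hour report to the coordinating center. An example is a hospitalization for a grade 2 gastrointestinal event that the site judges expected. The secondary safety endpoint counts gastritis, fistula, enteritis and ulcer from grade 2, and Section 9.1.3 sets the SBRT dose at 40 Gy in 5 fractions, against 33 Gy in 5 fractions in the group's own phase II study. Early notice of serious events in that category is therefore of some value.
- **Grade 3 SAEs.** Section 11.1.1 requires them within 24 hours, while 17.5.1 sends grade 3 events to the site log. The expected rate behind the Bayesian guideline in 17.5.1 is for grade 3 or higher toxicity, and that monitoring is meant to be continuous. Grade 3 events should not wait for a request.

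Sites also lack a clear statement of what counts as a late report.

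**Working it through.** **1. Figures bearing on size.** Section 2.2 reports for one single-fraction 25 Gy study: "7 (47%) experienced Grade 2 or greater GI toxicity, with 2 (13%) of the 15 experiencing Grade 3 or greater GI toxicity". This reproduces: 7/15 = 46.7% and 2/15 = 13.3%. By subtraction 7 − 2 = 5 patients were at grade 2. The denominator is the 15 patients alive more than 6 months after SBRT. The documents do not say how many of the 5 events were serious. For the five-fraction 33 Gy study, 17.5.1 gives only a grade 3–4 rate (8%). No count of missed reports can be derived, so the rest of the check compares the text.

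**2. The threshold in each place.**

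| Place | What goes promptly | What happens below the threshold |
|---|---|---|
| 11.1 definition | Not a reporting rule; SAE set by outcome, any grade | – |
| 11.1.1 | SAEs of grade 3 and above, 24 hours | Not stated |
| 11.2.1 table and note | SAEs from grade 3; UPs at any grade, 24 hours | Grade 1–2: UPs only |
| 17.5.1 | Grade 4 and higher | Grade 3 and lower: site log, on request |
| Appendix V, code 1 | Any SAE (short label), 24 hours | – |

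The two hospitalization rows of the table have identical entries, so length of stay changes nothing and grade alone decides. The table does have cells for grade 1–2 events with hospitalization, so the plan foresees such cases.

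**3. Four test cases.**

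- *Grade 2 event, hospitalized, judged expected.* An SAE under 11.1. Not covered by 11.1.1 or the note. The table's grade 2 cell covers UPs only, and an expected event fails the first UP criterion. Section 17.5.1 sends it to the log. Result: no 24-hour report. Read literally, deviation code 1 would still record the omission as a safety deviation.
- *Grade 2 event, hospitalized, unexpected, related and harmful.* A UP, so reported within 24 hours under 11.2.1.
- *Grade 3 SAE.* Within 24 hours under 11.1.1, the table and the note. Logged and reported on request under 17.5.1. Result: contradictory.
- *Grade 4 SAE.* Prompt under every section.

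**4. Cross-references.** Section 17.5.1 points to a Section 11.2.3 for logged events and cites Section 11 under a different title from its present heading. The current Section 11.2 has only 11.2.1. This suggests, but does not prove, that 17.5.1 was not updated when Section 11 was.

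**The case against.** The strongest reply is that only the 24-hour clock is missing, not the report. Section 11.3 has adverse events of every grade assessed at each visit and each chemotherapy cycle and entered in REDCap case report forms that are to be kept current. Section 16.4 lists SAEs and AEs among the required entries and gives coordinating-center staff access to all sites' data. Section 11.5 provides calls every other month, and sites report SAEs to their own IRB under local rules. Section 17.4 has all adverse events reported to the monitoring board and the coordinating center, though according to the guidelines elsewhere in the protocol. This stands. A reader might infer that serious grade 1–2 events stay on a site log and are never seen centrally; the documents do not support that. Still, none of these routes sets a 24-hour limit, and 16.4.1 starts its two-monthly calls only once all sites are approved and enrolling.

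Second, the UP route is wider than it may look. An event can be unexpected in nature, severity or frequency; the SBRT risk text in 6.2.1 does not name ulcer or gastritis and says complication rates are hard to predict. This also stands in part: some grade 2 hospitalizations could qualify. But Section 2.2 describes grade 2 ulcers after SBRT, so a site could reasonably call one expected.

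Third, the cut-off is repeated consistently within Section 11 and looks deliberate; 17.5.1 speaks of adverse events or toxicities in general, and code 1 is only a pick-list label. The last point is fair, and the code alone would be weak evidence. The reading of 17.5.1 does not remove the conflict: every SAE is an adverse event, and that section makes no exception for serious ones at grade 3.

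Fourth, the grade 2 endpoint is fed by routine collection, and the 16-patient review and the expected toxicity rate use grade 3 or higher. No endpoint or stopping boundary has been shown to change if a grade 2 report comes later. This stands.

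**Conclusion.** The inconsistency is established from the text alone. One definition without a grade is followed by a grade 3 cut-off in 11.1.1, the table and its note, a grade 4 cut-off in 17.5.1, and a deviation label with no cut-off. Two consequences follow: a serious grade 1–2 event that is not a UP has no 24-hour report to the coordinating center, and a grade 3 SAE is handled differently according to the section a site follows.

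The size cannot be given as a number of events. A reader might infer from Section 2.2 that most earlier SBRT gastrointestinal toxicity was grade 2 and project a count of missed reports onto the 86 patients in the SBRT arm. The documents do not support that. The detailed grades come from small studies of 25 Gy in a single fraction; the proportions quoted above apply to patients alive beyond 6 months; no grade 2 figure is given for the five-fraction regimen; and grade 2 does not mean serious. The number could be zero.

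The conclusion assumes only that a grade 1–2 event can meet an 11.1 criterion, which the table's own cells allow. It concerns timely safety oversight and clear instructions to sites, not the primary analysis. The change is worth making because it is cheap.

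**What to change.** Reconcile the passages to one rule based on seriousness:

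- **11.1.1 and the note below the table:** delete the grade 3 qualifier, so that every event meeting the 11.1 definition is reported within 24 hours.
- **Reporting table:** give the grade 1 and grade 2 cells the same entry as the grade 3 cells, in both hospitalization rows.
- **17.5.1:** replace the sentences on grade 4 and higher and on grade 3 and lower with a statement that every event meeting the 11.1 definition is reported within 24 hours and that non-serious adverse events are recorded under 11.3. Correct the reference to Section 11.2.3.
- **Appendix V, code 1:** no change of wording is needed, since the label then agrees with the rule.

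Editing Section 11 alone would leave 17.5.1 in conflict with it. The cost is wording in four places, a notice to sites, and probably a small number of extra expedited reports for sites and the coordinating center. No sample size, endpoint or stopping boundary changes.
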